## 3.2 Exclusion Criteria

- 3.2.1 Patients who have had chemotherapy, radiotherapy or other KS directed therapy other than ART for HIV within 2 weeks before the initiation of study treatment.
- 3.2.2 Patients who have not recovered from immune related adverse events due to prior therapy (*i.e.*, have residual toxicities > Grade 1) with the exception of hypothyroidism managed by supplemental levothyroxine.
- 3.2.3 Patients who have received treatment with any other investigational agent within 4 weeks before initiation of study treatment.
- 3.2.4 Patients with known hypersensitivity to Chinese hamster ovary cell products or other recombinant human antibodies.
- 3.2.5 Patients who have a history of severe allergic, anaphylactic, or other hypersensitivity reactions to chimeric or humanized antibodies or fusion proteins.
- 3.2.6 Patients who have received treatment with systemic immunostimulatory agents

(including, but not limited to, interferon [IFN]- $\alpha$  or interleukin [IL]-2, pomalidomide, or immune checkpoint inhibitors) within 6 weeks before initiation of study treatment.

3.2.7 Patients who have received treatment with systemic immunosuppressive medications (including, but not limited to, prednisone, cyclophosphamide, azathioprine, methotrexate, thalidomide, and antitumor necrosis factor [anti-TNF] agents) within 2 weeks before initiation of study treatment.

- Patients who have received acute, low dose, systemic immunosuppressant medications (e.g., a one-time dose of dexamethasone for nausea) may be enrolled.
- The use of inhaled corticosteroids, and mineralocorticoids (e.g., fludrocortisone) for patients with orthostatic hypotension or adrenocortical insufficiency is allowed.

3.2.8 Patients who have a history or risk of autoimmune disease, including, but not limited to, systemic lupus erythematosus, rheumatoid arthritis, inflammatory bowel disease, vascular thrombosis associated with antiphospholipid syndrome, Wegener's granulomatosis, Sjögren's syndrome, Bell's palsy, Guillain-Barré syndrome, multiple sclerosis, autoimmune thyroid disease, vasculitis, or glomerulonephritis.

Note: the following will NOT be exclusionary:

- The presence of laboratory evidence of autoimmune disease (e.g., positive antinuclear antibody (ANA) titer or lupus anticoagulant) without associated symptoms
- Clinical evidence of vitiligo or other forms of depigmenting illness
- Mild autoimmunity not impacting the function of major organs (e.g., limited psoriasis)

3.2.9 Patients with uncontrolled intercurrent illness including, but not limited to, symptomatic congestive heart failure (New York Heart Association Class III or IV), unstable angina pectoris, cardiac arrhythmia, recent myocardial infarction (within the last 6 months). Patients with known history of treatment with cardiotoxic agents, including anthracyclines, should have a clinical risk assessment of cardiac function using the New York Heart Association Functional Classification.

3.2.10 Psychiatric illness/social situations that would limit compliance with study requirements.

3.2.11 Pregnant women are excluded from this study because the effects of NT-I7 on the developing human fetus are unknown. Because there is an unknown but potential risk for adverse events in nursing infants secondary to treatment of the mother with NT-I7, breastfeeding should be discontinued if the mother is treated with NT-I7.

- 3.2.12 Patients with a history of solid organ or allogeneic stem cell transplant.
- 3.2.13 Patients with continuing KS regression on ART alone. Stable disease allowed.
- 3.2.14 Patients with a prior or concurrent malignancy requiring active therapy.
- 3.2.15 Patients with active tuberculosis.
- 3.2.16 Patients who have a history of idiopathic pulmonary fibrosis, pneumonitis (including drug induced), organizing pneumonia (bronchiolitis obliterans, cryptogenic organizing pneumonia, etc.), or evidence of active pneumonitis on screening chest X-Ray. History of radiation pneumonitis in the radiation field (fibrosis) is permitted.

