### 2.1.2 Epidemiology of Kaposi Sarcoma

KS is an angioproliferative tumor associated with infection by Kaposi sarcoma-associated herpes virus (KSHV, also known as human herpesvirus 8 or HHV-8) ([Gao et al. 1996](#)). There are four established clinical variants of KS: (1) classic, (2) African (endemic), (3) AIDS-related, and (4) iatrogenic (typically transplant/immunosuppression-related). All four types have strong association with an incompetent immune system that is unable to control KSHV.

Classical KS was historically seen in older men (male-to-female ratio 3:1) of Mediterranean and Eastern European descent and is thought to be related to reduced control of KSHV in the setting of immunosenescence. There is evidence that it is related to inherited variations in immunomodulating genes ([Kaasinen et al. 2013](#); [Aavikko et al. 2015](#)). It is frequently slow-growing (although aggressive and disseminated cases are seen), and survival rates are estimated at 70-80 percent.

Human immunodeficiency virus (HIV) infection-related KS accounts for greater than 80% of KS in the United States ([Shiels et al. 2011](#); [Engels et al. 2008](#)). KS increases the risk of death by at least 2-fold in people with HIV. Although the incidence of AIDS-related KS in the US declined dramatically after the introduction of combination antiretroviral therapy (ART) in the early 1990s, the incidence of classic KS has remained relatively steady from 1975 – 2005. Survival rates from HIV-related KS are poorer than classic KS, despite improving substantially with the introduction of ART ([Armstrong, Lam, and Chase 2013](#)).

Iatrogenic KS is most commonly seen in solid-organ transplant recipients on immunosuppressive regimens, particularly those who receive cyclosporine A. It can present in both indolent and aggressive forms and is generally managed initially with withdrawal or modification of immunosuppression. Most cases of iatrogenic KS are seen in individuals with Mediterranean or African descent, again suggesting inherited variations in immunomodulation ([Moosa 2005](#)).

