### 3. PATIENT SELECTION

#### 3.1 Eligibility Criteria

- 3.1.1 Patients must have histologically confirmed Kaposi sarcoma.
- 3.1.2 Patients must have evaluable disease.  
Note: Kaposi sarcoma will be evaluated using a modified version (consistent with NCI studies) of the AIDS Clinical Trial Group (ACTG) Oncology Committee staging and response definitions for KS.
- 3.1.3 No upper or lower limit on the number of prior therapies or stage of disease. No prior systemic therapy (other than ART for HIV) or local therapy is required.
- 3.1.4 HIV-positive patients must have been on effective anti-retroviral (ART) therapy for at least 3 months prior to enrollment, with persistent KS affecting quality of life due to

either T1 disease or T0 disease with inadequate disease regression on ART alone.

3.1.5 HIV-positive patients must have undetectable HIV viral loads  $\leq$ 40 copies/mL measured using an FDA-approved commercial assay with lower limit of detection between  $\leq$ 20 copies/mL and  $\leq$  40 copies/mL.

3.1.6 Patients with visceral involvement must:

- Meet other eligibility criteria
- Have any/all associated tumor associated symptoms  $\leq$  Grade 2 by CTCAE criteria; and/or
- Require no immediate intervention (e.g., mild oozing of oral KS not an exclusion criteria)

3.1.7 Patients must provide newly obtained core, punch, or excisional biopsy of a tumor lesion obtained up to 28 days prior to treatment initiation. An archival tumor sample obtained within 1 year of screening is allowed if pre-treatment biopsy is deemed unsafe or technically not feasible.

3.1.8 Patients must be  $\geq$ 18 years of age on day of signing informed consent document. Because no dosing or adverse event data are currently available on the use of NT-I7 in patients  $<$ 18 years of age, children are excluded from this study but will be eligible for future pediatric trials.

3.1.9 ECOG performance status  $\leq$ 2 (Karnofsky  $\geq$ 60%, see [Appendix A](#)).

3.1.10 Patients must have adequate organ and marrow function as defined below:

- leukocytes	$\geq$ 2,500/mcL
- absolute neutrophil count	$\geq$ 1,000/mcL
- platelets	$\geq$ 100,000/mcL
- hemoglobin	$\geq$ 9/dL
- total bilirubin	$\leq$ 1.5 institutional upper limit of normal (ULN) OR $<3 \times$ institutional ULN for Gilbert's syndrome or HIV protease inhibitors
- AST(SGOT)/ALT(SGPT)	$\leq$ 2.5 $\times$ institutional ULN
- creatinine	$\leq$ 2 $\times$ institutional ULN OR

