### 9.4 Analysis of Secondary Endpoints

#### 9.4.1 Objective Response Rate (ORR) to NT-I7 in HIV-positive and HIV-negative adults with KS

To preliminarily evaluate the objective response rate of KS to NT-I7 across all dose levels, KS response will be assessed according to modified ACTG criteria. For primary analysis the best response obtained within 12 months of the first dose of NT-I7 will be used, in all participants administered across study doses. Subset analyses for participants by dose level, HIV status, baseline CD4 greater than or less than 200 cells/uL, and history of prior chemotherapy for any subset in which there are at least 6 participants. A more precise estimate of efficacy will occur in a RP2D expansion cohort where dosing will be uniform. An expansion cohort will be included in an amendment.

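### Exclusion 3.2.13 bars entry with regressing KS only when the regression is on ART alone, so residual shrinkage after recent chemotherapy can be counted as an NT-I7 response

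*Combined protocol and SAP*

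**What the plan says.** **Entry rules on disease course.**
- Section 3.2.13 excludes "Patients with continuing KS regression on ART alone. Stable disease allowed".
- Section 3.1.4 applies to HIV-positive patients only. It asks for at least 3 months of effective ART "with persistent KS affecting quality of life due to" either T1 disease, or T0 disease that has not regressed adequately on ART alone.
- HIV-negative patients have no corresponding rule.

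**Entry rules on prior therapy.**
- Section 3.1.3: "No upper or lower limit on the number of prior therapies or stage of disease".
- Section 3.2.1 excludes those given "chemotherapy, radiotherapy or other KS directed therapy other than ART for HIV within 2 weeks before the initiation of study treatment".
- Sections 3.2.3 and 3.2.6 set longer intervals for investigational agents (4 weeks) and immunostimulatory agents (6 weeks).

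**How response is counted.**
- Appendix D, section 1.1, places the entry examination no more than 2 weeks before treatment. Section 2 of that appendix calculates response from baseline.
- Section 12.1.2.3 defines partial response by a decrease of at least 50% in lesion number or size, or flattening of at least half of the raised lesions, among other criteria. These must last at least 4 weeks.
- Section 9.4.1: "For primary analysis the best response obtained within 12 months of the first dose of NT-I7 will be used", in all treated participants and across doses. It plans subsets, including one by history of prior chemotherapy, where a subset has at least 6 participants.

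**The concern.** The existence of 3.2.13 shows that the authors saw the problem: if KS is already shrinking when NT-I7 starts, later shrinkage cannot be credited to NT-I7. The rule deals with one source of that shrinkage. For a patient who stopped chemotherapy 3 weeks ago, regression is not on ART alone, so the rule does not apply.

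Such patients are to be expected. Section 2.1.2 says many people with KS need intermittent treatment for life, mostly chemotherapy. Section 2.1.4 says advanced KS is usually treated first with liposomal anthracyclines.

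The trial has no control arm and no attribution rule, so a carried-over response looks the same as a drug response and can only push the ORR up. The T-cell endpoints have a related exposure. Section 2.1.5 notes that anti-neoplastic treatment can cause prolonged CD4+ depletion, and recovery from that would appear as fold-change from the pre-dose value.

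**Working it through.** **1. Is the gap closed elsewhere?** Take an HIV-positive patient with T1 disease, on ART, whose last chemotherapy was 3 weeks before dose 1 and whose lesions are still shrinking.
- 3.1.3: any number of prior therapies, so eligible.
- 3.1.4: met by T1 disease with persistent KS. The T1 limb says nothing about trajectory.
- 3.2.1: 3 weeks exceeds 2 weeks, so eligible.
- 3.2.13: regression is not on ART alone, so not excluded.

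An HIV-negative patient with the same history passes as well, without having to meet 3.1.4.

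**2. What must happen for the shrinkage to count?** Shrinkage before the entry examination is already in the baseline. Residual shrinkage alone must give a further 50% decrease (or 50% flattening) and hold for 4 weeks without progression. At a constant weekly proportional rate r, halving by week w needs r = 1 − 0.5^(1/w):
- by week 9 (first scheduled post-dose assessment): 7.4% per week
- by week 18: 3.8% per week
- by week 36: 1.9% per week

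This is demanding but not excluded, and the 12-month best-response window leaves time for it.

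**3. The denominator.** Section 9.2 gives up to 20 participants. Three dose levels × 6 + 2 replacements = 20, which matches, although the protocol does not spell out this derivation. With no DLT at any level the path is 3 + 3 + 6 = 12.

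**4. Effect of one carried-over response on the ORR.**
- N = 20: 1/20 = 5.0 points
- N = 18: 1/18 = 5.6 points
- N = 12: 1/12 = 8.3 points
- smallest reportable subset, N = 6: 1/6 = 16.7 points

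If NT-I7 had no activity, 1, 2 or 3 such cases in 20 would be reported as follows (Clopper-Pearson 95% intervals):
- 1 case: 5% (0.1–24.9%)
- 2 cases: 10% (1.2–31.7%)
- 3 cases: 15% (3.2–37.9%)

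**5. How often?** The documents give neither the share f of participants recently off chemotherapy nor the chance q that residual regression reaches partial response. Purely as an illustration, assume f = 10–50% and q = 10–40%. The spurious ORR is f × q:
- low: 0.10 × 0.10 = 1%, or 0.2 of 20; P(at least one) = 1 − 0.99^20 = 18%
- middle: 0.25 × 0.20 = 5%, or 1 of 20; P = 1 − 0.95^20 = 64%
- high: 0.50 × 0.40 = 20%, or 4 of 20; P = 1 − 0.80^20 = 99%

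The range is too wide to serve as an estimate. It shows only that the effect could be anything from negligible to dominant.

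**6. Does the planned chemotherapy subset resolve it?** Only in part. The never-treated half is free of chemotherapy carry-over, but it is reported only if it reaches 6. If most participants have had chemotherapy, the only reported half is the one that mixes recent with remote treatment.

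**The case against.** The strongest case against is that several provisions limit the problem and that little depends on the ORR.

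- **Shrinkage must still qualify.** A reader might infer that any shrinkage after chemotherapy will be scored as response. The documents do not support that: it must meet a partial-response criterion from entry and last 4 weeks. It can be counted, and once it qualifies nothing removes it.
- **Immunosuppressants.** A reader might see a second route of equal weight, because section 2.1.2 says iatrogenic KS "is generally managed initially with withdrawal or modification of immunosuppression" and 3.2.7 lists "Patients who have received treatment with systemic immunosuppressive medications" within 2 weeks. But 3.2.7 excludes recent use and does not require withdrawal. Section 2.1.2 describes iatrogenic KS as most common in solid-organ transplant recipients, whom 3.2.12 excludes, and 3.2.8 excludes most autoimmune disease. This route is minor.
- **T-cell analysis.** A reader might infer that fold-change ignores prior treatment. Section 9.4.3 tabulates it by prior systemic therapy and adjusts the model for prior therapy. Only recency is missing.
- **Local therapy.** Section 12.1.1.1 asks for marker lesions never treated locally, which largely protects lesion area. Lesion counts and flattening are not protected.
- **Low stakes.** ORR is secondary, with no null value or decision threshold, and 9.4.1 defers a more precise estimate to an expansion cohort.

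All of this stands and lowers the weight of the point. None of it prevents a participant still regressing after recent systemic KS therapy from entering and being counted.

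**Conclusion.** The gap is real and worth closing as a cheap improvement. The size that can be stated without assumptions is per case: 5 points of ORR at N = 20. No frequency, and so no expected bias, can be derived from the documents. A reader might take the illustrative range above as an estimate; it rests wholly on assumed inputs.

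The DLT and MTD assessment is unaffected. The T-cell side deserves some care, because section 6 defines the maximum effective dose by peripheral and intratumor T-cell levels and uses it to select the RP2D. With at most 6 participants per level, recovery after recent chemotherapy in one of them could blur that comparison. The documents give no basis for sizing this.

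**What to change.** **Analysis (main change).**
- In 9.4.1, add a sensitivity ORR that excludes, or reports separately, participants whose last KS-directed systemic therapy ended within a window before dose 1. State the window before the data are examined, and do not apply the minimum of 6.
- In 9.4.3, define the existing prior-therapy covariate by recency, or repeat the ALC and T-cell fold-change without those participants.
- Record the end date of the last KS-directed therapy as a data item. Sites already need it to apply 3.2.1.

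**Eligibility.** Extend 3.2.13 to continuing regression after any prior KS-directed therapy, with stable disease still allowed. Judge it from treatment history and pre-screening records as well as the screening examination. The change from Screening to Week 0 should not decide it alone: the study calendar and Appendix D allow both examinations within 2 weeks of dosing, section 12.1 acknowledges observer variability, and Week 0 falls after registration.

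**Cost.** One phrase in eligibility, one line in each of two analysis sections, and no change to the planned enrolment. A few candidates may be deferred, and the sensitivity set will be small and descriptive. The amendment that section 9.4.1 foresees for the expansion cohort is a natural occasion.

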### **3.3 Inclusion of Women and Minorities**

Both men and women of all races and ethnic groups are eligible for this trial.

## **4. REGISTRATION PROCEDURES**

### **4.1 Investigator and Research Associate Registration with CTEP**

Food and Drug Administration (FDA) regulations and National Cancer Institute (NCI) policy require all individuals contributing to NCI-sponsored trials to register and to renew their registration annually. To register, all individuals must obtain a Cancer Therapy Evaluation Program (CTEP) Identity and Access Management (IAM) account at <https://ctepcore.nci.nih.gov/iam>. In addition, persons with a registration type of Investigator (IVR), Non-Physician Investigator (NPIVR), or Associate Plus (AP) must complete their annual registration using CTEP's web-based Registration and Credential Repository (RCR) at <https://ctepcore.nci.nih.gov/rcr>.

RCR utilizes five person registration types.

- IVR – MD, DO, or international equivalent;
- NPIVR – advanced practice providers (e.g., NP or PA) or graduate level researchers (e.g., PhD);
- AP – clinical site staff (e.g., RN or CRA) with data entry access to CTSU applications such as the Roster Update Management [RUMS], OPEN, Rave, acting as a primary site contact, or with consenting privileges;
- Associate (A): other clinical site staff involved in the conduct of NCI-sponsored trials, and
- Associate Basic (AB): individuals (e.g., pharmaceutical company employees) with limited access to NCI-supported systems.

Documentation Required	IVR	NPI VR	AP	A	AB
FDA Form 1572	✓	✓			
Financial Disclosure Form	✓	✓	✓		
NCI Biosketch (education, training, employment, license, and certification)	✓	✓	✓		
GCP training	✓	✓	✓		
Agent Shipment Form (if applicable)	✓				
CV (optional)	✓	✓	✓		

RCR requires the following registration documents:

An active CTEP-IAM user account and appropriate RCR registration is required to access all CTEP and Cancer Trials Support Unit (CTSU) websites and applications. In addition, IVRs and NPIVRs must list all clinical practice sites and Institutional Review Boards (IRBs) covering their practice sites on the FDA Form 1572 in RCR to allow the following:

- Addition to a site roster,
- Assign the treating, credit, consenting, or drug shipment (IVR only) tasks in OPEN,
- Act as the site-protocol Principal Investigator (PI) on the IRB approval, and
- Assign the Clinical Investigator (CI) role on the Delegation of Tasks Log (DTL).

In addition, all investigators acting as the Site-Protocol PI (investigator listed on the IRB approval), consenting/treating/drug shipment investigator in OPEN, or as the CI on the DTL must be rostered at the enrolling site with a participating organization.

Additional information is located on the CTEP website at <https://ctep.cancer.gov/investigatorResources/default.htm>. For questions, please contact the **RCR Help Desk** by email at [[contact]](mailto:[contact]).

## 4.2 Site Registration

Permission to view and download this protocol and its supporting documents is restricted and is based on person and site roster assignment housed in the CTSU Regulatory Support System (RSS).

This study is supported by the NCI Cancer Trials Support Unit (CTSU).

## IRB Approval

For CTEP and Division of Cancer Prevention (DCP) studies open to the National Clinical Trials Network (NCTN) and NCI Community Oncology Research Program (NCORP) Research Bases after March 1, 2019, all U.S.-based sites must be members of the NCI Central Institutional

Review Board (NCI CIRB). In addition, U.S.-based sites must accept the NCI CIRB review to activate new studies at the site after March 1, 2019. Local IRB review will continue to be accepted for studies that are not reviewed by the CIRB, or if the study was previously open at the site under the local IRB. International sites should continue to submit Research Ethics Board (REB) approval to the CTSU Regulatory Office following country-specific regulations.

Sites participating with the NCI CIRB must submit the Study Specific Worksheet (SSW) for Local Context to the CIRB using IRB Manager to indicate their intent to open the study locally. The NCI CIRB's approval of the SSW is automatically communicated to the CTSU Regulatory Office, but sites are required to contact the CTSU Regulatory Office at [[contact]](mailto:[contact]) to establish site preferences for applying NCI CIRB approvals across their Signatory Network. Site preferences can be set at the network or protocol level. Questions about establishing site preferences can be addressed to the CTSU Regulatory Office by email or calling [name].

In addition, the Site-Protocol Principal Investigator (PI) (*i.e.*, the investigator on the IRB/REB approval) must meet the following five criteria in order for the processing of the IRB/REB approval record to be completed:

- Holds an Active CTEP status;
- Active status at the site(s) on the IRB/REB approval (*applies to US and Canadian sites only*) on at least one participating organization's roster;
- If using NCI CIRB, active on the NCI CIRB roster under the applicable CIRB Signatory Institution(s) record;
- Includes the IRB number of the IRB providing approval in the Form FDA 1572 in the RCR profile;
- Lists all sites on the IRB/REB approval as Practice Sites in the Form FDA 1572 in the RCR profile; and
- Holds the appropriate CTEP registration type for the protocol.

